7.1.2 QTc stopping criteria

If a clinically significant finding is identified (including, but not limited to changes from Baseline in QT interval corrected using Fridericia's formula [QTcF]) after enrollment, the Investigator or qualified designee will determine if the participant can continue in the study and if any change in participant management is needed. This review of the electrocardiogram (ECG)

printed at the time of collection must be documented. Any new clinically relevant finding should be reported as an AE.

A participant who develops an ECG finding which meets the bulleted criterion based on the ECG readings after first study drug application will be withdrawn from study medication.

- QTcF >500 msec OR Uncorrected QT >600 msec

For participants with underlying bundle branch block, follow the discontinuation criteria listed below:

Baseline QTcF with Bundle Branch Block	Discontinuation QTcF Threshold with Bundle Branch Block
< 450 msec	> 500 msec
450 to 480 msec	≥ 530 msec

See the Schedule of Activities (Section 1.3) for data to be collected at the time of treatment discontinuation and follow-up and for any further evaluations that need to be completed.

7.1.3 Permanent and temporary study drug discontinuation due to other reasons

Study participants must be permanently discontinued from study medication (but not necessarily from the study) if any of the following occurs:

1. Study participant experiences a thromboembolic event.
2. Study participant requires an induction therapy with cyclophosphamide for management of acute flare of [REDACTED] or other severe manifestation of SLE, in the opinion of the Investigator.
3. Study participant requires an induction of therapy with an approved biological immune response modifier or an investigational drug (see Section 6.6).
4. Potential drug-induced liver injury (pDILI) and related to study medication in the opinion of the Investigator, regulators, or the Sponsor. Discontinuation of study treatment for abnormal liver function should be considered by the Investigator when a participant meets one of the conditions outlined in Figure 7-1 or if the Investigator believes that it is in best interest of the participant.
5. Study participant has an anaphylactic reaction related to study medication (fulfilling Sampson criteria as described in Section 10.14).
6. Study participant develops an active TB or NTM (see Section 8.2.6.3).

Study participants may be temporarily discontinued from study medication (but not necessarily from the study) if any of the following occurs, but may be restarted. Consultation with the Medical Monitor is advised before restart:

1. Study medication will be stopped if the study participant develops a medical condition (or laboratory abnormality or ECG change) that, in the opinion of the Investigator, compromises the study participant's ability to proceed with study medication or compromises the study

participant's safety. This includes clinically significant infections such as SARS-CoV-2 (see Section 8.2.7) and tuberculosis (Section 8.2.6.3). Caution should be taken to exclude a clinically significant infection in case of symptoms (see Section 8.3). Study participants must be closely followed up. In case of resolution of the event leading to interruption, study medication can be restarted after consultation with the Medical Monitor unless the event fulfills the criteria for permanent study drug discontinuation. In case of upcoming surgery, the time between the last infusion of study medication administered to the participant and the surgery should be at least 4 weeks (if possible 6 weeks). After surgery, study medication can be restarted once the proliferative phase of wound healing is completed.

2. If there is a positive pregnancy test, study medication will be held. If there is confirmed pregnancy, study medication must be discontinued until end of the pregnancy. In case the participant intends to breastfeed after a pregnancy, study medication must be further discontinued until end of breastfeeding (including pumping breast milk to feed to a child).
3. In case a study participant answers Question 9 of the PHQ-9 with [REDACTED] [REDACTED] and active suicidal ideation is confirmed as indicated by a positive response ("Yes") to Question 4 or 5 of the C-SSRS study medication application must be discontinued and study participant must be referred immediately to a mental health care professional for further clarification. Permanent study medication discontinuation should be considered based upon the Investigator's judgment of benefit/risk. Consultation with the Medical Monitor and/or the Sponsor Study Physician is advised upfront to restart.

In addition, a participant may discontinue study medication administration at any time at the discretion of the Investigator for safety, behavioral, compliance, or administrative reasons. However, the participant should be encouraged to stay in the study under observation, continuing to be followed for all regularly scheduled safety and efficacy assessments.

Investigators are advised to contact the Medical Monitor, whenever possible in advance, to discuss the potential impact on the further study conduct in case of study drug discontinuation.

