1.3 Schedule of activities

Table 1-2: Schedule of activities

Period	Scr	Treatment (all visits in Treatment Period ±3 days)													SFU ^a
Visit	V1	V2	V3	V4	V5	V6	V7	V8	V9	V10	V11	V12	V13	V14	V15
Week	Scr	Bsl	W4	W8	W12	W16	W20	W24	W28	W32	W36	W40	W44	EOT ^b	EOS
Day ^c	D-14 to -1 ^d	D1 ^c	D28	D56	D84	D112	D140	D168	D196	D224	D252	D280	D308	D336	D378
Procedures															
Written informed consent	X														
Genetic informed consent ^e	X														
Demographics and Baseline characteristics ^f	X							X							
Thrombophilia diagnostic ^{g,dd}		X													
Inclusion/exclusion criteria ^h	X	X ⁱ													
General medical/procedures history	X														
Medication history ^j	X														
Vaccination history ^j	X														
Concomitant medications (inc. vaccines)	X	X	X	X	X	X	X	X	X	X	X	X	X	X	X
Pregnancy serum test	X														

Table 1-2: Schedule of activities

Period	Scr	Treatment (all visits in Treatment Period ± 3 days)													SFU ^a
Visit	V1	V2	V3	V4	V5	V6	V7	V8	V9	V10	V11	V12	V13	V14	V15
Week	Scr	Bsl	W4	W8	W12	W16	W20	W24	W28	W32	W36	W40	W44	EOT ^b	EOS W54
Day ^c	D-14 to -1 ^d	D1 ^c	D28	D56	D84	D112	D140	D168	D196	D224	D252	D280	D308	D336	D378
Procedures															
Pregnancy urine test (for WOCBP) ^{k,dd}		X	X	X	X	X	X	X	X	X	X	X	X	X	X
Antimalarial blood levels ^{dd}	X	X						X						X	
Chest x-ray ¹	X														
12-lead ECG ^m	X	X	X					X						X	
Vital signs	X	X ⁿ	X ⁿ	X ⁿ	X ⁿ	X ⁿ	X ⁿ	X ⁿ	X ⁿ	X ⁿ	X ⁿ	X ⁿ	X ⁿ	X	X
Study participant Identification Card assigned		X													
Randomization		X													
Infection serology ^o	X														
IGRA TB Test (QuantiFERON [®] at central lab) ^{dd}	X ^p													X	
TB questionnaire	X	X			X			X			X			X	
Complete physical examination and anamnesis ^q	X	X	X	X	X	X	X	X	X	X	X	X	X	X	X

Table 1-2: Schedule of activities

Period	Scr	Treatment (all visits in Treatment Period ±3 days)													SFU ^a
Visit	V1	V2	V3	V4	V5	V6	V7	V8	V9	V10	V11	V12	V13	V14	V15
Week	Scr	Bsl	W4	W8	W12	W16	W20	W24	W28	W32	W36	W40	W44	EOT ^b	EOS
Day ^c	D-14 to -1 ^d	D1 ^c	D28	D56	D84	D112	D140	D168	D196	D224	D252	D280	D308	D336	D378
Procedures															
Study withdrawal and study medication discontinuation criteria review			X	X	X	X	X	X	X	X	X	X	X		
BILAG 2004 ^r	X	X	X	X	X	X	X	X	X	X	X	X	X	X	X
SLEDAI-2K ^r	X	X	X	X	X	X	X	X	X	X	X	X	X	X	X
S2K-RI50			X	X	X			X			X			X	
PGA ^r	X	X	X	X	X	X	X	X	X	X	X	X	X	X	X
CLASI	X	X	X	X	X			X			X			X	
TJC/SJC	X	X	X	X	X			X			X			X	

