25. Study participant should, if possible, stay on stable doses of the following other concomitant medications for the treatment of SLE during the study unless changes in these treatments are clinically indicated: analgesics, non-steroidal anti-inflammatory drugs (NSAIDs), 3-hydroxy-3-methyl-glutaryl-coenzyme A (HMG-CoA) reductase inhibitors (statins), angiotensin converting enzyme (ACE) inhibitors, and other anti-hypertensive drugs.

Prior/Concurrent clinical study experience

26a. Study participant has previously been randomized within this study or has previously been assigned to treatment with DZP in a study evaluating DZP.

27. Study participant has participated in another study of an IMP (and/or an investigational device) within the previous 12 weeks or 5 half-lives of the IMP whatever is longer (see [Table 6-7](#)) or is currently participating in another study of an IMP.

Diagnostic assessments

28a. Study participant has history of a suicide attempt within the 5 years prior to the Screening Visit or has had suicidal ideation in the past 6 months as indicated by a positive response ("Yes") to either Question 4 or Question 5 of the "Screening/Baseline" version of the Columbia Suicide Severity Rating Scale (C-SSRS) at Screening.

Note:

- In case a study participant responds to Question 9 in Patient Health Questionnaire-9 (PHQ-9) [REDACTED] the severity of [REDACTED] the suicidal ideation needs to be adequately assessed with the C-SSRS rating scale.

– In case of history of a suicide attempt more than 5 years ago the absence of concurrent suicidal ideation and/or severe depression should be confirmed by a mental healthcare practitioner before enrolling into the study.

29a. Study participant has ≥ 3 times the ULN alanine aminotransferase (ALT), aspartate aminotransferase (AST), or alkaline phosphatase (ALP), or $>$ ULN bilirubin ($\geq 1.5 \times$ ULN

bilirubin if known Gilbert's syndrome), except in the case where the abnormal test values are ascribed to SLE hepatitis

- If study participant only has >ULN, but <1.5xULN bilirubin, fractionate bilirubin to identify possible undiagnosed Gilbert's syndrome (ie, direct bilirubin<35%) should be assessed, except in the case where the abnormal test values are ascribed hemolytic anemia, in the opinion of the Investigator.
- In case of a suspected SLE hepatitis, eligibility must be discussed with the Medical Monitor.

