8 STUDY ASSESSMENTS AND PROCEDURES

Study procedures and their timing are summarized in the Schedule of Activities ([Table 1-2](#)).

Protocol waivers or exemptions are not allowed.

Immediate safety concerns should be discussed with the Medical Monitor or the Sponsor Study Physician immediately upon occurrence or awareness to determine if the participant should continue or discontinue study treatment.

Adherence to the study design requirements, including those specified in the Schedule of Activities, is essential and required for study conduct.

All screening evaluations must be completed and reviewed to confirm that potential participants meet all eligibility criteria. The Investigator will maintain a screening log to record details of all participants screened and to confirm eligibility or record reasons for screening failure, as applicable.

Procedures conducted as part of the participant's routine clinical management (eg, blood count) and obtained before signing of the ICF may be utilized for screening or baseline purposes provided the procedures met the protocol-specified criteria and were performed within the time frame defined in the Schedule of Activities.

The amount of blood collected from each participant over the duration of the study will be approximately 900mL. Additional extra assessments that may be required for re-screening, technical issues with the collected samples or safety evaluations may result in additional blood volume to be collected.

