- The Investigator may change his/her opinion of causality in light of follow-up information and send a SAE follow-up report with the updated causality assessment.
- The causality assessment is one of the criteria used when determining regulatory reporting requirements.

Follow-up of AEs and SAEs

- The Investigator is obligated to perform or arrange for the conduct of supplemental measurements and/or evaluations as medically indicated or as requested by UCB to elucidate the nature and/or causality of the AE or SAE as fully as possible. This may include additional laboratory tests or investigations, histopathological examinations, or consultation with other health care professionals.
- An AE should be followed until it has resolved, has a stable sequelae, the Investigator determines that it is no longer clinically significant, or the participant is lost to follow up. This follow-up requirement applies to AEs, SAEs, and AEs of special interest.
- If a participant dies during participation in the study or during a recognized follow-up period, the Investigator will provide UCB with a copy of any post-mortem findings including histopathology.
- New or updated information will be recorded in the originally completed eCRF.
- The Investigator will submit any updated SAE data to the Sponsor within 24 hours of receipt of the information.

Reporting of SAEs

SAE Reporting to UCB via an Electronic Data Collection Tool

- The primary mechanism for reporting an SAE to UCB will be the electronic data collection tool.
- If the electronic system is unavailable for more than 24 hours, then the site will use the paper SAE data collection tool (see next section).
- The site will enter the SAE data into the electronic system as soon as it becomes available.
- After the study is completed at a given site, the electronic data collection tool will be taken off-line to prevent the entry of new data or changes to existing data.
- If a site receives a report of a new SAE from a study participant or receives updated data on a previously reported SAE after the electronic data collection tool has been taken off-line, then the site can report this information on a paper SAE form (see next section) or to the UCB Study Physician by telephone.
- Contacts for SAE reporting can be found in SERIOUS ADVERSE EVENT REPORTING.

SAE Reporting to UCB via Paper CRF

- Facsimile transmission of the SAE paper CRF is the preferred method to transmit this information to the UCB Study Physician.

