Exclusion	28a	
Study participant has history of a suicide attempt within the 5 years prior to the Screening Visit or has had suicidal ideation in the past 6 months as indicated by a positive response ("Yes") to either Question 4 or Question 5 of the "Screening/Baseline" version of the Columbia Suicide Severity Rating Scale (C-SSRS) at Screening.
 
Note:
 
 • In case a study participant responds to Question 9 in PHQ9 [REDACTED] [REDACTED] [REDACTED] [REDACTED] [REDACTED] the severity of the suicidal ideation needs to be adequately assessed with the C-SSRS rating scale • In case of history of a suicide attempt more than 5 years ago the absence of concurrent suicidal ideation and/or severe depression should be confirmed by a mental healthcare practitioner before enrolling into the study. 	To protect study participants' well-being. Study participants with SLE have an increased risk for depression and suicidality. Some biotherapeutic immunomodulators are suspected to increase the risk for suicidality.

Criterion	N	Content	Justification
Exclusion	29a	
Study participant has ≥ 3 times the ULN alanine aminotransferase (ALT), aspartate aminotransferase (AST), or alkaline phosphatase (ALP), or $>$ULN bilirubin ($\geq 1.5 \times$ULN bilirubin if known Gilbert's syndrome), except in the case where the abnormal test values are ascribed to SLE hepatitis.
 
 • If study participant only has $>$ULN, but $<1.5 \times$ULN bilirubin, fractionate bilirubin to identify possible undiagnosed Gilbert's syndrome (ie, direct bilirubin $<35\%$) should be assessed, except in the case where the abnormal test values are ascribed to SLE hepatitis or hemolytic anemia, in the opinion of the Investigator. • In case of a suspected SLE hepatitis, eligibility must be discussed with the Medical Monitor. • If study participant has a result of ALT, AST, or ALP that is $>$ULN but that does not meet the exclusion limit at Screening, a repetition of the lab assessment is recommended to judge the dynamic of the increase but is in the Investigator's discretion considering the medical history of the study participant. In case of a further clinically relevant increase (with a value that still doesn't meet the exclusion limit), inclusion of the study participant must be discussed with the Medical Monitor. 	To protect study participants' well-being. Severe liver dysfunction could impact the metabolism of DZP

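### The only suicidality-specific mandatory drug stop and mental-health referral needs the PHQ-9 and C-SSRS to agree, so a C-SSRS intent or plan answer alone, or suicidal behavior, is left to Investigator judgment

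*Protocol*

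**What the plan says.** Protocol 7.1.3 lists reasons for permanent and for temporary discontinuation of study medication. The six permanent reasons include no suicidality entry. Item 3 of the temporary list starts from an answer to PHQ-9 Question 9, whose qualifying levels are blacked out. It continues "and active suicidal ideation is confirmed as indicated by a positive response" (a Yes) to C-SSRS Question 4 or 5. When both hold, dosing must stop and the "study participant must be referred immediately to a mental health care professional for further clarification". Permanent discontinuation is then to be considered on benefit and risk, and consultation is advised before restart.

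Protocol 8.2.5 makes the C-SSRS the on-study instrument for suicidal ideation and behavior, but attaches no action to any result. Table 1-2 schedules both the PHQ-9 and the C-SSRS at every visit. SAP 10.4.4 numbers the behavior categories: 6 preparatory acts, 7 aborted attempt, 8 interrupted attempt, 9 actual non-fatal attempt, 10 completed suicide.

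The general routes to a stop are these:

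- Temporary item 1 of 7.1.3: "Study medication will be stopped if the study participant develops a medical condition" that, in the Investigator's opinion, compromises safety or the ability to proceed. Close follow-up is required.
- The closing text of 7.1.3 allows a stop at the Investigator's discretion.
- Section 8 asks that immediate safety concerns be taken to the Medical Monitor or Sponsor Study Physician "immediately upon occurrence or awareness to determine if the participant should continue or discontinue study treatment".
- Table 1-2 has a row "Study withdrawal and study medication discontinuation criteria review" marked from Week 4 to Week 44.

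**The concern.** The C-SSRS is the dedicated suicidality assessment. Section 8.2.5 has it done by trained personnel, preferably the Investigator or Subinvestigator, using all available information. The PHQ-9 is described in 8.1.2.6 as a depression screening tool. Under 8.1.2 it is self-completed, is to be administered by staff other than the treating physician, and is checked only for completeness. A rule that needs both lets a self-reported screening answer block the mandatory effect of the dedicated assessment. It also leaves suicidal behavior out, because the C-SSRS limb names Questions 4 and 5 only.

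Appendix 13 justifies the entry criterion on suicidality partly by the disease: "Study participants with SLE have an increased risk for depression and suicidality". With approximately 230 sites planned, an intent or plan answer, or an attempt, could be handled differently from site to site when no rule names it.

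**Working it through.** No sample-size, power or error-rate arithmetic applies. The check is the logic of the rule, set beside the schedule and the general routes.

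**The rule.** Let P be a qualifying PHQ-9 Question 9 answer, I a Yes to C-SSRS Question 4 or 5, and B a Yes to any of C-SSRS categories 6 to 9. The readable trigger is P and I.

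- P and I, with or without B: stop and referral are mandatory.
- I without P, with or without B: not triggered.
- B without I, with or without P: not triggered.

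**Can the untriggered cases arise?** Yes. The word confirmed suggests that the C-SSRS was meant as a follow-up to Question 9, but Table 1-2 schedules it at every visit regardless. SAP 10.4.4 has it cover the time since the last visit at Visits 2 to 15.

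**Where would the rule apply?** The C-SSRS is given at 13 post-Baseline visits (V3 to V15). SAP 10.2 plans 12 infusions; less the Baseline infusion, 12 - 1 = 11 are post-Baseline (V3 to V13), matching the 11 visits marked for review of discontinuation criteria. At these, both the stop and the referral matter. At the other 13 - 11 = 2 visits (Weeks 48 and 54), only the referral matters.

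**What can the redactions change?** The blackout in item 3 sits in the Question 9 answer slot. If any non-zero answer qualifies, the first gap shrinks to participants who deny Question 9 entirely but report intent or plan on the C-SSRS. However broad P is, the second gap stays, because the readable C-SSRS limb does not include behavior. Section 8.3.7 (AEs of special monitoring) has no readable body and could narrow either gap.

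**Does another route require the same action?**

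- Item 1 and the discretionary stop depend on judgment and name no C-SSRS result.
- Section 8 calls for discussion, not a hold.
- The visit review applies whatever criteria exist.
- Section 8.5 gives a suicide attempt by overdose as an example of an AE or SAE, and SAEs go to the Sponsor within 24 hours (8.3.1). That is reporting.
- Appendix 3 obliges the Investigator to arrange medically indicated evaluations to clarify an event's nature or cause: "This may include additional laboratory tests or investigations, histopathological examinations, or consultation with other health care professionals". Consultation is possible, not required, and mental health is not named.

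No readable route outside item 3 mandates mental-health referral.

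**The case against.** The strongest reply is that the protocol already handles these cases and that the deciding words cannot be read. Item 1 is more than permissive once the Investigator judges safety to be compromised. The person who hears a C-SSRS Yes is preferably the Investigator or Subinvestigator, so usually someone who can stop dosing and refer. Appendix 3 has an intentional overdose with possible suicidal intent reported whatever its consequences, and under 8.4 the Study Physician reviews SAEs continuously. On this view, what remains is a preference for an algorithm over clinical judgment.

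Much of this stands. A reader might infer that someone who attempts suicide on study could go on being dosed with nothing in the protocol to prevent it. The documents do not support that: several routes lead to a stop. They do not guarantee the same action for the same C-SSRS result, and they do not require referral.

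A reader might also take the mismatch with entry as an error. Exclusion 28a acts on a suicide attempt within 5 years alone, or on a participant who "has had suicidal ideation in the past 6 months as indicated by a positive response" to C-SSRS Question 4 or 5 at Screening, with no PHQ-9 condition. But entry limits stricter than on-study stops are normal here: ALT at 3 times the upper limit of normal excludes at entry, while on study ALT alone reaches a stopping criterion at 8 times, or lower if persistent. The comparison supports the point without proving it. So does Section 8.2.6.1.2, where an IGRA conversion brings a mandatory stop and prompt specialist referral; that is a laboratory test, not an interview.

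Nor does the readable text show a suicidality signal specific to DZP. Appendix 13 cites the disease and a suspicion about some immunomodulators, which supports referral more directly than a drug hold.

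**Conclusion.** The point holds as a gap in a pre-specified safety trigger. On the readable text, C-SSRS Question 4 or 5 Yes with a non-qualifying PHQ-9 answer, and suicidal behavior without both limbs, carry no mandatory stop or referral of their own. The behavior gap is the firmer one, since the redacted answer slot cannot fill it. The size of the first gap is unknown.

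No count of participants can be given. Counting the logical patterns that the rule misses would not measure it either, because the patterns are not equally likely or equally serious.

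The conclusion assumes that no redacted text, in item 3 or Section 8.3.7, supplies the missing trigger. On that basis this is a worthwhile, inexpensive patient-safety improvement, held with medium confidence. It is not evidence that participants were left without protection.

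**What to change.** Reword temporary item 3 of 7.1.3 so that a Yes to C-SSRS Question 4 or 5, or to any of categories 6 to 9, triggers immediate mental-health referral at any post-Baseline visit, including Weeks 48 and 54, and a temporary study-drug hold while on treatment, regardless of the PHQ-9 answer. Leave out the separate C-SSRS question on non-suicidal self-injury. Keep PHQ-9 Question 9 as a prompt for C-SSRS assessment, and keep the existing sentences on restart and permanent discontinuation.

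The cost is one reworded sentence and no new assessments. The downside is additional temporary holds and referrals, in a number that cannot be derived. Protocol 9.6 counts permanent discontinuation of study medication as non-response and does not name temporary holds. However, SAP 5.1 refers to Section 4.3 for the algorithm that dates discontinuation, and that section is redacted, so the effect of a long or late hold on the primary endpoint cannot be checked.
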